Continuous data (e.g. age) will be summarised using means and standard deviations, whereas categorical data (e.g. gender) will be summarised using percentages. Medians and quartiles will be reported for non-parametric data, and means, standard deviations and 95% confidence intervals for normally-distributed parametric data. Normality of continuous data will be assessed using histogram plots and the Shapiro Wilk Test. For each measure, the difference between arms will be examined

Ida Telecare

IRAS: 232078

using parametric (e.g. T-test) or non-parametric (e.g. Wilcoxon Rank Sum Test) statistics where appropriate. For categorical data, Chi-square test will be used, and Fishers exact test if any of the cells are less than 5. Statistical significance will be set at $p=0.05$ and corrected (e.g. Bonferroni) for multiple comparisons. As outcome data will be collected after the intervention period, no interim analyses will be performed.

2. *Patient and Audiologist views and experiences*

For the alternative pathway only:

A sub-set (6/28) of hearing assessment appointments will be video recorded to enable a detailed assessment of how the tools were jointly used by the patient and audiologist. The videos will also be shared with the research funders to identify how the tools might be improved or amended to better suit patients' needs in future.

A sample of patients and audiologists will be recruited from the alternative pathway using maximum variation sampling (Patton 1990), to take part in semi-structured interviews with a member of the research team. Interviews will examine patients and audiologists perceptions and experiences of using the 'Why Improve My Hearing?' telecare tool, specifically:

- what influenced patients use of the tool
- how, when and where the tool was used by patients in preparation for their hearing assessment appointment
- how the tool was used jointly by audiologists and patients within the clinical appointment
- what benefit(s) patients and audiologists attributed to use of the tool

The interview schedules will be designed to provide an in-depth understanding, and will be reviewed by patient representatives to ensure clarity of concepts and relevance to patients. Data collection will cease once data saturation has been reached.

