7.2. Sampling

7.2.1. Size of sample

Sub-study 1: Feasibility

- Quantitative: Not applicable

One of the main aims of this Arm is to identify recruitment rates/intervention take-up in this population.

- Qualitative:
 - Think Aloud n=6-8 patients

Data collection will cease once data saturation has been reached. A sample size of 6-8 has been found to be generally sufficient to achieve data saturation for Think Aloud techniques (Henshaw et al. 2017).

- Semi-structured interviews with patients and audiologists: $n \leq 15$

Data collection will cease once data saturation has been reached (Guest et al. 2006).

Sub-study 2: Effectiveness

- Quantitative: n=56 participants (n=28 per arm)

In order to detect a 10% change in MARS-HA (smallest possible change) at a power of 80% and type II error rate of 5%, a total of 50 participants are required, 25 in each arm. This was calculated using a standard deviation for global MARS-HA scores derived from (Ferguson et al. 2016). As outcome measures will be taken immediately post-assessment, it is expected that fewer than usual participants will fail to complete outcome measures. Hence, a conservative attrition rate of 15% has been used, thus accounting for attrition, a total of 56 participants (28 per arm) will be recruited.

Ida Telecare

IRAS: 232078

- Qualitative: Semi-structured interviews with patients and audiologists

Data collection will cease once data saturation has been reached.

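### The 80% power is claimed for one MARS-HA test at an unadjusted 5% level, but section 5 corrects for multiple comparisons without naming a primary outcome or exempting MARS-HA

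*Protocol*

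**What the plan says.** **Sample size (Protocol, section 7.2.1).** The target is one measure: "In order to detect a 10% change in MARS-HA (smallest possible change"). The error rates are given as "at a power of 80% and type II error rate of 5" per cent, and the result is "a total of 50 participants are required, 25 in each arm". The number is raised to 28 per arm for attrition. The SD is taken from a cited study and is not printed. No adjusted significance level is mentioned. The paragraph on attrition places the outcome measurement immediately after the hearing assessment.

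**Analysis (Protocol, section 5, Sub-study 2, part 1).** The testing rule covers all outcomes alike: "For each measure, the difference between arms will be examined". The threshold is then set: "Statistical significance will be set at $p=0.05$ and corrected (e.g. Bonferroni) for multiple comparisons".

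**Outcomes (same section).** Eight measures are listed immediately after the assessment: MARS-HA, PAM, ECHO, SPaRQ, HHIE, GHABP Part I, stage of readiness and the outpatient survey. Eight are listed 10-12 weeks after fitting: hearing aid uptake, hearing aid use, MARS-HA, SPaRQ, HHIE, GHABP Part II, SADL and PAM. MARS-HA, ECHO and SADL each have four subscales or composite scores. The example schedule in Appendix 2 is shorter: four questionnaires at the initial assessment and four measures at follow-up.

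Neither section calls any outcome primary. The objectives in section 4.1 list uptake, use, self-efficacy and readiness together.

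**The concern.** The two sections use different significance levels for the same comparison. Section 7.2.1 gives MARS-HA the whole 5%. Section 5 makes it one of several tests that share the 5%, and does not say how many.

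A sample size that gives 80% power at 5% gives less at any stricter level. A tool that has the planned effect on self-efficacy could therefore be reported as having no significant effect far more often than the one time in five that the protocol implies. Because the family is undefined, the threshold for the outcome that sets the sample size is also open. It could be settled after the data are seen.

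**Working it through.** **Inputs**
- 25 evaluable per arm, 1:1, 80% power (section 7.2.1).
- Significance level 5%. Section 7.2.1 prints this as "type II error rate of 5" per cent. With 80% power the type II rate is 20%, so I read it as type I. Sidedness is not stated; I assume two-sided.
- SD: not given. The standardised effect d is therefore back-solved. The loss of power needs only d, not the SD.
- Number of tests m: 4 (one visit in the Appendix 2 example schedule), 8 (one time point in section 5, or both visits in Appendix 2), 16 (both time points in section 5). Subscales are not counted.

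**Step 1. The plan's own figure.** Without the SD, 25 per arm cannot be reproduced independently. Taking it as correct, the normal formula gives

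d = (z₀.₉₇₅ + z₀.₈₀) × √(2/n) = (1.960 + 0.842) × √(2/25) = 0.792.

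The t-test version (noncentral t, 48 degrees of freedom) gives d = 0.809. By construction this returns 80% at m = 1.

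**Step 2. Power under Bonferroni.** Each test is made at 0.05/m. In the normal approximation,

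power = Φ(d√(n/2) − z₁₋₀.₀₂₅/ₘ), with d√(n/2) = 2.802.

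| m | level | z | normal power | t-test power | missed (t-test) |
|---|---|---|---|---|---|
| 1 | 0.05 | 1.960 | 80.0% | 80.0% | 20.0% |
| 4 | 0.0125 | 2.498 | 61.9% | 60.6% | 39.4% |
| 8 | 0.00625 | 2.734 | 52.7% | 50.5% | 49.5% |
| 16 | 0.003125 | 2.955 | 43.9% | 41.1% | 58.9% |

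**Step 3. Other evaluable numbers (t-test).** With all 28 per arm evaluable, power is 67.0%, 57.4% and 48.0% for m = 4, 8 and 16. With the planned 15% lost from 56 (56 × 0.85 = 47.6, or 23.8 per arm), it is 57.8%, 47.7% and 38.3%.

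**Step 4. Sidedness.** If the 5% was one-sided in both places, d = 0.713, and power at 25 per arm is 47.7% for m = 8 and 37.8% for m = 16. The conclusion does not depend on the two-sided reading.

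**Step 5. What the correction would require.** To keep 80% power at d = 0.81, the trial needs about 36 per arm for m = 4, 41-42 for m = 8 and 46-47 for m = 16, against 25 stated.

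**Step 6. In points, under a further assumption.** If the 10% change means 10 points on the 0-100 scale, the implied SD is 10/0.809 = 12.4. At 25 per arm, the difference detectable with 80% power then rises from 10 points to 13.0 (m = 8) or 13.9 (m = 16).

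**The case against.** **The family is not defined and Bonferroni is an example.** This stands, and it limits the size of the claim. The correction could run over one visit, both visits or subscales. Holm also fits the wording and loses less power if other measures show effects, although MARS-HA still faces 0.05/m under Holm if it is the first to be rejected. A reader might infer that power simply falls to 40-50%. That range assumes Bonferroni over the 8 to 16 measures of section 5. The shorter Appendix 2 schedule, taken one visit at a time, gives 61%.

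**A reader might also infer that a true effect would probably be missed.** The figures do not support that in general. With 8 tests, power is 50.5% at 25 per arm and 57.4% at 28; with 4 tests at 25 per arm it is 60.6%. A miss becomes the likelier result only with the larger family, or with 8 tests and fewer than 25 evaluable per arm.

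**A statistical analysis plan could name MARS-HA as primary.** If it did, and exempted it from correction, the loss would vanish. But the protocol does not leave multiplicity to a later document. It states a rule, and that rule has no exemption.

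**The trial is preliminary and the correction is conservative.** Both are true: the risk is a missed effect, not a false claim. The protocol nevertheless makes an 80% power claim and plans significance tests, so the two should agree.

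**Conclusion.** The point holds. The 80% in section 7.2.1 is power for one uncorrected MARS-HA test; section 5 prescribes a corrected one, with no primary outcome and no exemption. The stated power therefore does not apply to the analysis as written.

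The direction is certain, but the size is conditional. Under Bonferroni with 25 evaluable per arm, power is about 61%, 51% or 41% for 4, 8 or 16 tests, so the chance of missing an effect of the planned size is roughly 40-60% instead of 20%. Counting subscales would lower power further; a step-down method could soften the loss.

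The figures assume a two-sided 5% type I level and d = 0.81 back-solved from the stated size and power. The figures in points also assume that 10% means 10 points.

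**What to change.** In section 5, state that global MARS-HA immediately after the hearing assessment is the single primary outcome, tested at two-sided 5% without correction. This is the time point that section 7.2.1 refers to. Make all other measures and time points secondary, including MARS-HA at 10-12 weeks. Report them as differences between arms with 95% confidence intervals, or apply Holm within a stated secondary family.

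This is a change of wording and needs no extra participants or data, but it should be made before any outcome data are analysed. The cost is that the secondary measures, including readiness, uptake and use, carry no confirmatory claim. The team has to accept this knowingly, because section 4.1 lists those outcomes alongside self-efficacy.

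If the team prefers to keep the correction over all measures, section 5 should define the family and the method, and section 7.2.1 should restate the power at the corrected level. At the present size that is about 41-61% under Bonferroni for 4 to 16 tests. Holding 80% would take about 36 to 47 evaluable participants per arm.

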Interview schedules have been created by the research team and will be reviewed by patient representatives to ensure questions are clear and relevant to patients. Data collection will cease once data saturation has been reached. A sample size of $n \leq 15$ has been found to be generally sufficient to achieve data saturation for semi-structured interviews (Guest et al. 2006).

Interviews will be audio recorded and anonymously transcribed verbatim. Transcripts will be analysed by the research team using inductive thematic analysis. Generated codes and themes relating to benefit(s) of the interventions and additional suggested content will be organised using the TDF and mapped to the COM-B system to examine how the telecare tools might influence health behaviours according to individuals’ Capability, Opportunity and Motivation.

Sub-study 2: Effectiveness

1. Impact of the ‘Why Improve My Hearing?’ Ida telecare tool

Enrolled patients to this sub-study will be minimised to one of two arms: (i) treatment-as-usual, patients receiving standard care only, and (ii) experimental pathway, patients receive standard care plus access to the Ida Telecare ‘Why Improve My Hearing?’ tool online prior to their first assessment. Minimised allocation will be based on gender (male/female) and age: younger (<70 years old)/older (70 years old or greater). The minimisation will be generated and maintained by a researcher not directly involved in patient recruitment or testing (EH, [name]), using OxMaR software (O’Callaghan 2014).

The following validated outcome measures will be completed online or via post in accordance with the patients’ preference:

Baseline – before completion of the ‘Why Improve My Hearing?’ Ida telecare tool and immediately post hearing assessment appointment:

- *Measure of Audiologic Rehabilitation Self-efficacy for Hearing Aids (MARS-HA)* (West and Smith 2007). Includes four subscales: basic handling, advanced handling, adjustment to hearing aids, and aided listening skills. Respondents indicate how confident they are that they

could do the things described on an 11-point scale (0%=cannot do this, to 100%=certain I can do this).

- *Short-form Patient Activation Measure (PAM)* (Hibbard et al. 2005). A 13-item measure that assesses patient knowledge, skill, and confidence for self-management of their health. Each item is scored on a four-point ordinal scale (0 = disagree strongly to 3 = agree strongly).

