Interviews with patients and audiologists will be audio recorded and anonymously transcribed verbatim. Transcripts will be subjected to inductive thematic analysis by the Study Co-ordinator, guided by the research questions. Generated codes and themes will be categorised according to the TDF and mapped to the COM-B system to examine if, and if so how, the intervention prompted changes in health behaviours relative to individuals' Capability, Opportunity and Motivation.

Ida Telecare

IRAS: 232078

Study timeline

	2017					2018							
	study	Sep	Oct	Nov	Dec	Jan	Feb	Mar	Apr	May	Jun	Jul	Aug
Study set-up and recruitment													
Seek approvals (Ethics/sponsor)	■												
Study setup	■	■											
NAS Audiologist briefing		■											
Recruitment of NAS direct referral patients		■	■	■	■	■	■						
Feasibility													
Quantitative data collection (initial assessment)			■	■	■	■	■	■					
Quantitative data collection (fitting)				■	■	■	■	■	■				
Qualitative Think Aloud & concurrent analyses						■	■	■	■	■			
Quantitative data collection (follow-up)							■	■	■	■	■	■	■
BCT Taxonomy coding								■	■	■			
Qualitative semi-structured interviews									■	■	■		
Qualitative interview transcription & analysis										■	■	■	
Quantitative data analysis										■	■	■	
Write-up and dissemination											■	■	■
Effectiveness													
Quantitative data collection (initial assessment)			■	■	■	■	■	■					
Qualitative semi-structured interviews						■	■	■	■				
Qualitative analysis using COM-B									■	■	■		
Quantitative data collection (6-weeks post-fit)						■	■	■	■	■	■	■	■
Quantitative data analysis											■	■	■
Write-up and dissemination												■	■

Data Storage and Access

All data will be stored in password protected databases (e.g. SPSS) or files on a secure part of the NIHR Nottingham BRC network that is accessed only by members of the research team. All paper files will be stored in locked cupboards within the NIHR Nottingham BRC. Audio and video recordings will be securely stored electronically for a period of no more than 18 months. Arrangements will be made for the confidential destruction of these recordings within 6 months of the planned study end-date of 31st August 2018.

Anonymised data arising from this research may be shared with other genuine researchers.

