11.2. Appendix 2 – Schedule of Procedures (Example)

Procedures ^a Feasibility arm ^b Effectiveness arm	Visit			
	Pre-initial assessment	Initial assessment	Fitting	Follow-up
Informed consent (post) ^{a,b}	x			

Ida Telecare

IRAS: 232078

Demographics and History questionnaire (post) ^{a,b}	x			
Observation of treatment (phone/email/post) ^a	x	x	x	x
Observation of treatment (phone/email/post) ^b	x			
Think Aloud ^a	x			
MARS-HA ^b		x		
PAM ^b		x		
ECHO ^b		x		
HHIE ^b		x		
Hearing aid data logging ^b				x
GHABP ^b				x
IOI-HA ^b				x
SADL ^b				x
Semi-structured interviews ^{a,b}				x

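### Filming and patient interviews take place in the experimental arm only; filming comes just before the post-assessment questionnaires, and interview order relative to the 10-12 week outcomes is not fixed

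*Protocol*

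**What the plan says.** Section 5 of the protocol, under sub-study 2, defines the two arms as "i) treatment-as-usual, patients receiving standard care only, and (ii) experimental pathway, patients receive standard care plus access to the Ida Telecare" tool. By that definition, access to the tool is the only difference between them.

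The qualitative part of sub-study 2 is introduced with "For the alternative pathway only". From the content and the denominator of 28, this means the experimental arm. Two activities follow:

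- Filming: "A sub-set (6/28) of hearing assessment appointments will be video recorded to enable a detailed assessment of how the tools were jointly used" by patient and audiologist. The protocol adds that the recordings will be shared with the funder.
- Interviews: "A sample of patients and audiologists will be recruited from the alternative pathway using maximum variation sampling". Topics include "how the tool was used jointly by audiologists and patients within the clinical appointment" and the benefits that patients attribute to the tool. No number of interviews is given; they continue until saturation.

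Outcome questionnaires are completed at baseline, then "immediately post hearing assessment appointment", then 10-12 weeks after hearing aid fitting. MARS-HA is collected at all three times. Section 7.2.1 sizes the trial on MARS-HA and refers to outcomes taken straight after the assessment.

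In the study timeline, the Effectiveness row "Qualitative semi-structured interviews" is marked January-April 2018 and post-fitting data collection January-August 2018. Appendix 2 marks the interviews under the follow-up visit, beside hearing aid data logging, GHABP and SADL, and gives no order among them.

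**The concern.** The arm comparison is meant to estimate the effect of access to the tool. Part of the experimental arm also receives research attention that no control receives. Being filmed, with the recording going to the organisation that makes the tool, may change how the patient and audiologist behave in the appointment. The patient then completes the self-report questionnaires. Similarly, a patient who has just been asked to reflect on the tool's benefits may rate self-efficacy or satisfaction differently a few weeks later.

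The planned analysis is a simple two-group test for each measure. Any shift caused by filming or interviewing would therefore be counted as an effect of the tool. Hearing aid uptake and logged use are less exposed, because they do not rely on self-report.

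**Working it through.** **Order of events**

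| Activity | Arm | Relative to post-assessment questionnaires | Relative to 10-12 week questionnaires |
|---|---|---|---|
| Filming | Experimental, 6 of 28 | Directly before | Before |
| Patient interviews | Experimental, number open | After (they ask about the appointment and are held at the research centre) | Not fixed |

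For the interviews, 10 weeks is 70 days. Counting back from 30 April 2018, the end of the interview bar, gives 19 February 2018. A patient fitted after that date and interviewed within the bar is interviewed before the 10-week point. Initial-assessment collection runs to March, so such patients can exist. Patients assessed in October-December could reach follow-up inside the bar. The timeline labels the later outcome as 6 weeks post-fit, not 10-12. On that label (42 days) the date becomes 19 March, and the order is still open.

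**The plan's own figure**

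Inputs from section 7.2.1: target difference 10 points, 80% power, 25 per arm. I take a two-sided 5% type I error. The SD comes from a cited study and is not stated, so 25 per arm cannot be reproduced. It can only be inverted.

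- Normal formula: SD = 10 × √(25/2) / (1.960 + 0.842) = 12.6.
- Noncentral t: SD = 12.4 (12.37 unrounded to one decimal), used below.

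**Size of a filming effect**

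Share filmed = 6/28 = 0.214. Shift in arm mean = 0.214 × assumed effect per filmed patient.

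| Assumed effect (points) | Shift in arm mean | False-positive rate if the tool does nothing (28 vs 28) |
|---|---|---|
| 2 | 0.43 | not computed |
| 5 | 1.07 | 6.2% |
| 10 | 2.14 | 9.8% |

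The nominal rate is 5%. For filming alone to produce the 10-point target, each of the six would have to move by 10/0.214 = 46.7 points.

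**Power without the filmed patients** (all others complete, SD 12.37)

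- 28 vs 28: SE = 12.37 × √(1/28 + 1/28) = 3.31; 10/SE = 3.03; power 84%.
- 22 vs 28: SE = 12.37 × √(1/22 + 1/28) = 3.52; 10/SE = 2.84; power 79%.

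No figure is computed for the interviews, because sub-study 2 does not say how many patients will be interviewed.

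**The case against.** The strongest reply is one of proportion. Evaluating the process in the intervention arm alone is normal in a mixed-methods trial, and controls have no tool use to film or discuss. Patients know whether they were given the tool, so expectancy already affects all 28 experimental patients; filming six adds little. The trial claims only preliminary evidence. The assumed 5-10 points is half to all of the target difference, and no document supports an effect that large. Nor is the direction known: a camera could make patients anxious or constrain the consultation. All of this stands, and it keeps the point modest.

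The timing objection also stands in part. The timeline shows calendar bars for the whole study, not the order within a patient. Interviewing early enrollees at follow-up would satisfy both the timeline and Appendix 2, which is itself headed as an example. A reader might infer that the two contradict each other, or that most interviews come before the final questionnaires. Neither is shown. What is shown is that no rule prevents an early interview.

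Finally, a sensitivity analysis may sit in a statistical analysis plan that is not at hand, so its absence from the protocol is not a fault. The one-arm filming and the open interview order are set in the protocol itself.

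**Conclusion.** The point holds as a modest one-arm co-exposure. Filming affects 21% of the experimental arm just before the outcome used for sample size. Interviews may affect an unstated share before the later self-reported outcomes. Under an assumed 5-10 point filming effect, the arm mean shifts by 1.1-2.1 MARS-HA points against a target of 10. Size and direction are unknown, and the false-positive and power figures rest on an SD implied by the stated sample size.

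Three stronger readings are tempting but unsupported:

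- That the attention effect cannot be separated from the tool. The six filmed patients are identifiable and 22 of 28 are unfilmed.
- That the interviews contaminate the post-assessment outcomes. They follow those questionnaires.
- That up to 15 of the 28 patients are interviewed. That ceiling is given for sub-study 1 only, where the sample-size section applies it to patients and audiologists together.

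**What to change.** 1. State that no sub-study 2 patient is interviewed until that patient's final outcome questionnaire has been returned. Say what applies to a patient who is not fitted with a hearing aid or does not return it.
2. Align the Effectiveness interview row of the timeline with Appendix 2, and state in Appendix 2 that the interview follows the follow-up questionnaires.
3. Pre-specify, in the protocol or the analysis plan, a sensitivity analysis of the arm comparison without the filmed patients, and say how the six are chosen. If they are volunteers, dropping them from one arm introduces some selection, so this should support the full comparison and not replace it.

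Moving the filming to sub-study 1 is not a good substitute: those patients use whichever tools they wish, may not choose this one, and are outside the randomised pathway.

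The changes are to wording; the number of recordings and interviews stays the same. The cost is later interviews with longer recall of the assessment appointment. If late-fitted patients are included, the qualitative analysis row (April-June) may have to move as well. The sensitivity analysis gives up about 5 percentage points of power, in that analysis only.
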